7.1.7 Management and retention of the cohort

Each Clinical Center will develop its own administrative structure for managing the cohort and for retaining study subjects. In developing this structure and for all contacts with study subjects, confidentiality will be of paramount importance. Each Clinical Center will determine a study name and address that does not indicate the nature of the project. In addition, because of possible unauthorized mail-opening, any communications will be worded so as to not reveal the

nature of the appointment or other indicated contact. Telephone messages will be similarly cryptic.

The major means of ensuring the continued cooperation of study subjects will be personal contact with individuals on the study staff. Frequent telephone communication with the subjects will inform and remind them of scheduled visits. The contact person will be easily accessible to the subjects by telephone and will facilitate their interactions with other study personnel and, where possible, with the subjects' sources of care. Patients will receive reminders by mail before visits and notes after each visit. Other forms of contact such as newsletters and social gatherings may also serve to foster compliance and to provide the study with a "face". The study Executive Committee (See Section 14) will review each center's plan for fostering compliance and will review data on missed visits that will be provided by the Coordinating Center.

Study personnel should be able to provide useful services to subjects. Such services might include referrals to various community support organizations, welfare agencies, and discussions of HIV-related therapies. In addition, compliance enabling devices may be of considerable benefit. Examples include provision of taxi fares or other means of transportation, scheduling visits at times convenient for the subject (such as after work hours), and having an easily accessible site for conducting the evaluations. In some instances paying an honorarium for each visit may improve subject cooperation.

Contact with heroin addicts who are in methadone treatment programs will be facilitated by developing close liaisons with the treatment program personnel. Hiring of "street-wise" interviewers and outreach workers will also serve to maintain compliance for this group.

Compliance will also be achieved by maintaining regular contact with the subject's primary physicians if the subject agrees. At the time of enrollment in the study the subject's primary physician will be provided with a written summary of the protocol and a schedule of follow-up visits. After each visit a summary of the results of the evaluation will be sent to the physician (with the subject's authorization).

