The potential value of screening asymptomatic HIV seropositive subjects for the presence of P. carinii is of great interest to both investigators and clinicians. For example, Brenner and associates (ref 29, Section 3) found improved short and long term survival in patients with P. carinii pneumonia that was diagnosed after July, 1985 compared with survival in patients diagnosed before that date. They attributed the improvement to earlier diagnosis, at a time when the disease was less severe. However, this would not explain improved long term survival, and, it is possible that lead-time bias accounted for the apparent increased longevity. Alternatively, early treatment may minimize the impact of P. carinii pneumonia on the overall course of the HIV disease. The present study seeks to evaluate this latter possibility by intensively screening a randomly selected subset of subjects and comparing subsequent morbidity and mortality with these variables in a routinely evaluated group.

Clearly, new information leading to a broader understanding of the pulmonary diseases that are associated with HIV infection would be of major importance with relevance to both clinical and epidemiologic aspects of HIV disease. Both predictors and patterns of pulmonary diseases will be identified, enabling more accurate empiric diagnoses and earlier therapy. The data will also be useful in planning for long term management of patients and assessing the magnitude and types of resources necessary in the future. As with most natural history studies, questions will be raised that can then be addressed more specifically by targeted studies.

5. Study Design

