7.2.4 Diagnostic evaluation of symptoms or findings suggestive of lung disease

All diagnostic evaluations will be performed in the Clinical Centers and will follow the algorithms devised for purposes of the protocol (Section 7.2.7). The diagnostic evaluation may be triggered by the occurrence of symptoms (noted either at the time of a scheduled evaluation or between evaluations) or by chest radiograph detected on scheduled screening examinations. Standard methods to be used for each of the studies are described in Appendix 5. All data will be recorded on standard forms.

The symptoms that will trigger an evaluation include:

Table 6
Schedule of Interval Laboratory Studies

Frequency of studies (months)
(See text for definitions of group)

Study	Group A-1(1)	Group A-2	Group B-1(1)	Group B-2	Group C(1)	1-month F/U (all groups)(2)
History Performance status	6	3	6	3	6	+
Physical Exam	6	3	6	3	6	+
CBC/Diff, platelets	6	3	6	3	6	+
ESR/SMA	6	3	6	3	6	+
Absolute CD-4 CD-8, CD-3(4)	6	3	6	3	6	+
Serum Bank	6	3	6	3	6	+
HIV Ab(3)	Entry	Entry	Entry	Entry	6	0
Induced Sputum	Entry	Entry	Entry	Entry		
Skin tests	12	12	12	12	12	0
PFT	12	3	12	3	12	+
CXR (PA/Lat)	12	3	12	3	12	+

(1) Subjects enrolled in Group A-1 or B-1 who later develop an HIV-related pulmonary complication will continue the same schedule, except PFT's will be performed every 6 months. The schedule of evaluations for Group C subjects who seroconvert will not change.

(2) "+" = test performed.

(3) Omit if documented positive prior to study entry.

(4) May be omitted if performed within the three months prior to visit.

1) unexplained cough that persists for more than five days;
2) unexplained breathlessness (progressive over ≥ 5 days or severe ≥ 1 day); or 3) unexplained new onset of documented fever ($\geq 38^{\circ}\text{C}$ oral ≥ 5 days). As a part of the orientation and at each routine clinic visit, each study subject will be alerted to these symptoms and instructed to contact the study office should they develop. For each of these symptoms, if a reason other than a possible HIV-related pulmonary process can be found (e.g., asthma), the evaluation will not proceed. If the subject has fever with localizing extrapulmonary symptoms (e.g., diarrhea) and no pulmonary symptoms, the evaluation will not proceed, and the subject will be referred to the primary physician. Any diagnoses resulting from such an episode will be entered at the subsequent visit on the Interval Visit Questionnaire.

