table analyses of 2 or higher dimensions will be constructed to assess statistically whether or not the different pulmonary diseases tend to occur together or whether they are basically independent. Chi-square tests for association will be appropriate in this situation. Simple adjustment for single confounding variables may be made by Mantel-Haenzel methods and more complicated adjustments will be done by loglinear modelling.

Question 12 is, "Does diagnosis of P. carinii pneumonia by intensive screening decrease both short-and long-term mortality?" All seropositive patients will be included in this analysis and the major comparison of interest will be the intensively screened patients versus those who have been randomized to routine evaluations. Since this is a randomized substudy, there is much less concern about selection bias than for the other questions of interest which involved nonequivalent groups. In this case the principal predictive variable of interest is intensive or routine screening and the outcome is short and long term mortality. Variables confounding the interpretation of the analysis include various forms of treatment which patient may be on. To explore question 12, Kaplan Meier survival curves (or Cox regression if covariables must be dealt with) will be computed and statistically compared. In the calculation of the curves it will be important to take the origins of the survival curve as the time of randomization in order to avoid length biased sampling. Additionally, based on back extrapolation of the slope of decline of CD-4 cell counts the approximate time of HIV infection can be estimated and used as the starting point for the curves.

If the answer to question 12 is "No", one may well wish to investigate the reasons for the lack of impact of the intensive effort. A logical inquiry in this regard is whether or not the lead time between onset of preclinical disease and symptoms is sufficient to permit a significant alteration of the disease process. In this regard, extensions to methodology of Zelen and Feinleib, [Biometrika, 1969, pp.601-614] may be useful in estimating the lead time from incidence and prevalence data from the intensive and routine study arms.

10. Quality Control

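### The arms of the PCP screening substudy also differ in visits, blood tests and feedback to physicians, so an arm difference is the effect of the intensive follow-up package and not of earlier PCP diagnosis alone

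*Protocol*

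**What the plan says.** **Aim.** Section 4 (Rationale) raises the possibility that early treatment lessens the impact of PCP on the course of HIV disease, and continues: "The present study seeks to evaluate this latter possibility by intensively screening a randomly selected subset of subjects". Section 5 gives the feasibility and impact of early PCP diagnosis as the reason for randomising Groups A and B. Question 12, in Section 9 and Appendix 1, asks: "Does diagnosis of P. carinii pneumonia by intensive screening decrease both short-and long-term mortality". Questions 13 and 14 ask the same about hospital days and performance status.

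**Schedule.** In Table 6 (Section 7.2.4) the columns run A-1, A-2, B-1, B-2, C, in months; A-2 and B-2 are intensive. The chest film row reads "CXR (PA/Lat) 12 3 12 3 12", and pulmonary function tests have the same intervals. The blood count row reads "CBC/Diff, platelets 6 3 6 3 6" and the lymphocyte subset row "CD-8, CD-3(4) 6 3 6 3 6". History, examination, chemistry and serum banking are also 3 against 6 months. Footnote 4 says of the subsets: "May be omitted if performed within the three months prior to visit".

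**Feedback.** Section 7.1.7 says "After each visit a summary of the results of the evaluation will be sent to the physician", subject to the subject's authorization. It also names discussion of HIV-related therapies as a service study staff might offer. In Appendix 4, one center undertakes to write to the primary physician after each routine visit.

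**Therapy.** Section 6 says that treatment is not controlled and that this will confound the intensive-versus-routine comparison. It takes comfort from the near equivalence of treatment regimens. Appendix 1 lists antiviral and preventive therapy as confounders for Questions 12 to 14.

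**The concern.** The substudy is worded as if the arms differed only in how early PCP is found. They also differ in how often a subject is seen, has blood drawn and CD-4 counted, and in how often results may reach the prescribing physician. Section 3.3 reports that TMP-SMX prophylaxis reduced PCP and prolonged life, and that AZT lowers PCP incidence and severity. If closer monitoring brings either forward in the intensive arm, mortality could fall because PCP was prevented, not because it was found early.

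A favourable answer to Question 12, as worded, would then credit early diagnosis with an effect that may have come by another route. If the answer were unfavourable, the lead-time work planned at the end of Section 9 would use incidence and prevalence data from two arms whose underlying PCP risk may differ.

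The safeguards do not cover this route. Near-equivalent treatments for PCP say nothing about when prophylaxis or antiviral therapy begins in each arm. Therapy begun after randomisation may itself result from the arm. Adjusting for it can remove part of the effect and introduce bias.

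**Working it through.** **1. Scheduled contacts (Table 6).** Rounds = months of follow-up / interval.

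| | Intensive | Routine |
|---|---|---|
| Visits, blood count, chemistry, CD-4, 3 years | 36/3 = 12 | 36/6 = 6 |
| Same, 4 years | 48/3 = 16 | 48/6 = 8 |
| Chest film and lung function, 3 years | 36/3 = 12 | 36/12 = 3 |

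The 2:1 ratio is firm for visits, blood count and chemistry. For CD-4 it is only the schedule, because footnote 4 may narrow it. The Protocol Summary and Section 5 describe routine testing as 12-monthly; I follow Table 6, to which the note to Figure 1 refers for the tests.

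**2. The plan's own precision figure.** Appendix 3 assumes three-year mortality of 15% in A and 50% in B, so p = (0.15 + 0.50)/2 = 0.325. Table 5B gives 527 + 527 = 1,054 seropositive subjects, or 527 per arm.

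Half-width = 1.96 × √(2 × 0.325 × 0.675 / 527) = 0.0566, which reproduces the stated 6%. The precision figure is not in dispute.

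**3. Scale of the intended route.** Appendix 3 takes one-year PCP at 5% in A and 20% in B; Section 3.3 gives about 20% mortality for a first episode. Assuming constant annual rates:

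- three-year PCP: A 1 − 0.95³ = 14.3%; B 1 − 0.80³ = 48.8%; average 31.5%
- first-episode deaths: 0.315 × 0.20 = 6.3 points
- averting 25%, 50% or 100% of them: 1.6, 3.2 or 6.3 points

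Reaching 5.7 points through first episodes alone means averting 5.66/6.31 = 90% of those deaths. Adding recurrences at 35% (top of the range in Section 3.3) raises the total to 6.3 × 1.35 = 8.5 points and lowers the requirement to 66%. Neither figure is a ceiling, since Section 4 also hopes for a benefit beyond the episode.

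**4. Scale of the other route (assumed inputs).** Shift = 0.325 × (1 − RR) × difference in uptake between arms.

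- RR 0.8, 10 points: 0.325 × 0.2 × 0.10 = 0.7 points
- RR 0.5, 30 points: 0.325 × 0.5 × 0.30 = 4.9 points

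Neither the risk ratios nor the uptake differences come from the Protocol. The result shows only that this route could be of the same order as the intended one.

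**5. Illustration of CD-4 timing (assumed inputs).** Take a decline of 67 cells a year (Section 3.1 reports 65 to 70), starting counts of 300 to 400, lognormal measurement error with a CV of 15 to 30%, and 100,000 simulated subjects per setting. The first observed count below 200 comes on average 3.0 to 5.7 months earlier with 3-monthly than with 6-monthly counts. If routine subjects obtain half of the interim counts elsewhere, the gap is about 1.4 to 2.5 months. With no measurement error it is 0 or 3 months, depending on the starting count.

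**The case against.** Several points on the other side are sound.

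- Question 12 asks; it concludes nothing. Section 9 compares the randomised arms with survival measured from randomisation. That comparison is valid for the effect of assignment. What fails is the name given to the effect.
- Section 6 openly says that uncontrolled therapy will confound the arm comparison, calls complete treatment data essential, and says that failing this secondary objective would not greatly reduce the study's value. The hazard is disclosed, but its reassurance covers only equivalence of regimens, and differing monitoring and feedback are not mentioned.
- Results go out only with authorization, and Section 7.1.7 does not say that the summary includes CD-4.
- The study is not the source of primary care, and Appendix 4 recruits from AIDS clinics, an AZT trial and existing cohorts. Many subjects may have CD-4 counts from elsewhere, which would shrink the contrast.
- The Protocol makes no count of 200 a treatment trigger; Question 8 uses it only as an analysis category. The decline rate comes from men who did not develop AIDS or ARC. The 3.0 to 5.7 months is therefore illustrative and near the top of what is plausible.

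A reader might infer that the comparison is invalid, or that early detection may be credited only if therapy initiation and PCP incidence do not differ by arm. The documents support neither. Randomisation protects the package effect. Effective screening would itself bring earlier treatment of PCP and change diagnosed incidence through lead time, the lead-time analysis needs those incidence data, and a non-significant difference is not evidence of equality.

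**Conclusion.** The point holds as a mismatch between the stated aim and the contrast that the design delivers. The arm difference in mortality, hospital days and performance status is the effect of assignment to intensive follow-up. That package may include earlier prophylaxis or antiviral therapy, and the difference cannot by itself be attributed to earlier PCP detection.

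The firm quantity is the schedule: 12 against 6 visits and blood rounds over 3 years, with CD-4 possibly closer than that. The mortality shift of 0.7 to 4.9 points and the CD-4 timing gap rest on outside assumptions and do not show that the bias will occur. No sample-size or precision figure changes. The objective is secondary, but the correction alters what may be concluded from it and should be made.

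**What to change.** 1. Reword Questions 12 to 14 and the Section 5 aim as the effect of assignment to intensive versus routine follow-up.
2. Make the unadjusted arm comparison from randomisation the main analysis. Appendix 1 lists mode of diagnosis as the predictor and counts one-month mortality and hospital days from PCP diagnosis; the main comparison should use the arm as predictor and outcomes counted from randomisation.
3. Treat antiviral and preventive therapy started after randomisation as consequences of the arm, and remove them as adjustment variables from that comparison.
4. State in Section 6 that visits, blood monitoring and feedback to physicians also differ by arm.
5. Compare by arm the time from randomisation to first antiviral therapy and to first anti-pneumocystis prophylaxis begun before any PCP diagnosis, excluding treatment of PCP. Present this as descriptive support for interpreting an arm difference and the lead-time analysis, with no pass/fail condition.

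The cost is a narrower claim, some rewording, and a small analysis of treatment data that Section 6 already requires. The visit schedule and patient care do not change.

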7.2 Clinical Evaluations

All clinical evaluations will be performed in the Clinical Centers using uniform methods described in detail in Appendix 5. Each center will comply with the study quality control program (Section 10), thereby ensuring that results will be comparable among the centers.

7.2.1 Initial visit and assessment

The initial visit and assessment will be conducted as soon as possible after identification and recruitment of the subject, determination that he/she meets study criteria, and obtaining informed consent. During the initial visit, study procedures will be explained in detail. The symptoms that will prompt an evaluation will be reviewed carefully and the patient will be instructed to contact the Clinical Center should he/she note such symptoms. In addition to the discussion each subject will be given a card with a summary of the symptoms that should prompt a visit, the phone number of the Clinical Center and the names of the contact person, Principal Investigator, Study Coordinator and other relevant personnel.

The specific evaluations to be performed at the initial assessment include the following (methods described in Appendix 5):

- 1) History and physical examination;
- 2) Performance status;
- 3) Frontal and lateral view chest films;
- 4) Pulmonary function tests;
- 5) Hemoglobin, hematocrit, white blood cell, differential and platelet counts, erythrocyte sedimentation rate;
- 6) SMA 20 automated blood chemistry panel including serum lactate dehydrogenase;
- 7) HIV antibody test (previously known positive results from a qualified laboratory will be accepted);
- 8) Serum specimens to be frozen at -70°C for subsequent analyses (Appendix 8);
- 9) Determination of lymphocyte subsets (helper/inducer, cytotoxic/suppressor and mature circulating T cells);
- 10) Skin testing using tuberculin and mumps antigens (read by study staff or other qualified professional staff at 48 to 96 hours) (Appendix 9);

- 11) Induced sputum examined for P. carinii and mycobacteria (Group B only). Abnormalities detected during the initial assessment will be evaluated as described in the diagnostic algorithms, Section 7.2.7.

7.2.2 Frequency of follow-up evaluations

All subjects in Groups A and B will be assigned at random by the Coordinating Center to receive either routine (subgroups A-1 and B-1 and Group C) or intensive (subgroups A-2 and B-2) follow-up evaluations. Randomization will be accomplished at the Coordinating Center by a computer generated series of random numbers unique to each Clinical Center. Thus, there will be approximately even numbers in the subgroups in each Clinical Center as well as in the cohort as a whole.

7.2.3 Scheduled follow-up evaluations

Table 6 shows the evaluations to be performed and their frequencies in each of the groups. During these evaluations a modified history and physical examination will be done and the same series of laboratory tests as performed in the initial evaluation (except induced sputums) will be obtained. For purposes of data analysis subjects will be considered as belonging to the group to which they were originally assigned. Subjects in Groups A-1, B-1 and C who develop an HIV-related pulmonary process will continue to be followed at the same intervals except that pulmonary function tests will be performed every 6 months. HIV seronegative controls (Group C) will be followed at the same intervals as Groups A-1 and B-1. The schedule for Group C subjects who become HIV seropositive will not change.

